FHIR-ed Up for Tobacco Cessation NCT06292130

Unique Protocol ID: R43HL156588 December 15, 2024

Unique Protocol

Objective:

The purpose of this research was to assess in a 30-day pilot test the acceptability and feasibility of *refresh*, a theoretically-grounded, mobile-optimized, and individualized, tobacco cessation native iOS app. *refresh* is designed for adult tobacco users. The app is tailored to the user's readiness to quit smoking and it leverages Fast Healthcare Interoperability (FHIR) and HealthKit API calls to import data from AppleHealth that is used to personalize app content.

Design:

As this was a Phase I study, it entailed a single group, pre-post pilot test of the *refresh* app.

The *refresh* app experience has various components, including:

- Interactive activities designed to increase smokers' readiness to quit. Activities include goal setting; cigarette log and savings tracker; a "Crush Cravings" gamified tool; mindfulness, self-reflection, seeking support, dealing with temptations, etc.;
- Tailored text messages:
- A personalized actionable insight transmitted to the patient's electronic health record
 (EHR) that can be used to guide a clinician's interaction around tobacco during a patient
 appointment. The actionable insight includes customized insight to the patient's stage of
 readiness, current smoking rate, goal, and app use, along with a brief, 20-second
 message matched to the patient's readiness to quit that the clinician could deliver.

Methods:

Recruitment for the 30-day pilot test began in March 2022. Potentially eligible patients (i.e., who had an indication of tobacco use in Epic and an upcoming regularly scheduled appointment for a visit with one of the participating clinicians in the next 30—45 days) were identified by the Rush University Medical Center research assistant (RA). The RA then sent a secure message through their patient portal in Epic (i.e., MyChart) with an invitation to take part in the refresh study on behalf of the clinician the patient was scheduled to see. Up to 2 reminders were sent via MyChart and 1 reminder was made by phone in advance of the appointment. All invitations directed potential participants to a Rush-branded landing page, which began with a brief overview of the study, followed by "Frequently Asked Questions" that address several elements of informed consent. The landing page also included a link to a brief (about 5 minute) secure screener.

The study eligibility criteria assessed in the secure screener were:

- having an upcoming appointment with a participating clinician
- being age 18 or older;
- being a current smoker;
- having an iPhone 6s or higher or an iPad;
- being willing and able to download a mobile app;
- being able to read and speak English

The screener excluded individuals who did not meet the study eligibility criteria. Individuals who screened out or who do not consent to study participation were thanked for their time.

Eligible participants were invited to provide informed consent. Those who provided informed consent completed a baseline assessment that assessed smoking history, current rate of tobacco use, psychosocial expectancies, self-efficacy, and readiness to quit smoking, tobacco products, and e-cigarettes. They were invited to download and use the app for 30 days. As a thank you for taking part, participants received a \$25 gift card as a thank you for their time and were told that they could interact with the app as often as they like over the following 30 days. During that period, up to 11 re-engagement text and email messages were sent based on inactivity in the app.

In advance of the participant's next regularly scheduled appointment, data on the patient's readiness to quit, current smoking status, number of interactions with the app were synthesized into an actionable insight for their clinician that was combined with an evidence-based behavior change message that would be most helpful for the patient. This actionable insight was manually placed in the Epic pre-charting note before the visit by the Rush research assistant.

Participants received an email 30-days post-baseline to invite them to complete the follow-up assessment. Up to 9 emails and/or text reminders to complete the follow-up assessment were sent. Participants who failed to respond were called by a member of the study team and asked to complete the assessment by phone. Up to 2 attempts were made to reach them by phone. Participants received a \$25 Amazon.com gift card as a thank you for completing the follow-up assessment. Fifty-one individuals participated in the pilot test.

The modification of aims (i.e., reduction in sample size from 100 to 50 participants) was requested by the PI and approved by our Program Officer on 12/21/22. Similarly, the manual placement of the actionable insight into the EHR was an approved aim modification for Phase I.

Simple descriptive statistics were calculated to describe the study sample and to evaluate app utilization and acceptability. Paired t-tests of pre-post differences on several key outcomes, including the primary outcome (psychosocial expectancies) were conducted, and responses to open-ended data qualitatively coded.

## Statistical Analysis Plan

This study involved a single-group, pre-post design. Paired t-tests were used to determine the effect of the *refresh* intervention on the primary and secondary outcomes. The primary outcome was change, from pretest (baseline) to posttest (30 day follow-up), in psychosocial expectancies for smoking. Secondary outcome measures include change in confidence to quit smoking between pretest (baseline) and posttest (30 day follow-up) assessments. Cohen's d was used to assess the magnitude of the differences.

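### The SAP claims its paired t-tests determine the effect of refresh, which a single-group pre-post design cannot do

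*SAP*

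**What the plan says.** The Statistical Analysis Plan section opens with "This study involved a single-group, pre-post design". The next sentence reads "Paired t-tests were used to determine the effect of the *refresh* intervention on the primary and secondary outcomes". The section then defines the primary outcome as the change in psychosocial expectancies for smoking from baseline to 30 days, lists change in confidence to quit as a secondary outcome, and applies Cohen's d to the size of the differences.

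The Protocol is more careful. Its Objective begins "The purpose of this research was to assess in a 30-day pilot test the acceptability and feasibility of" the app, and its Design section says "it entailed a single group, pre-post pilot test of the" app. The last paragraph of Methods describes the same analysis neutrally: "Paired t-tests of pre-post differences on several key outcomes, including the primary outcome (psychosocial expectancies) were conducted". Methods also reports "Fifty-one individuals participated in the pilot test".

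Neither document provides a control arm, an external or historical comparator, repeated baseline measurements, or a statement limiting causal interpretation.

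**The concern.** The hypothesis tested is that the mean within-person change is zero. The question the SAP sentence says is answered is whether refresh changed the outcomes. With one group and two measurements these are different questions, because the observed change is the sum of any effect of refresh and any change from other sources.

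Several such sources are uncontrolled: the passage of time, the motivation that comes with volunteering, answering the same measures twice, regression to the mean, and the scheduled clinic visit. The visit arises from the recruitment route itself. Invitations went to patients with "an upcoming regularly scheduled appointment for a visit with one of the participating clinicians in the next" 30 to 45 days, while the follow-up invitation was sent 30 days after baseline, with reminders and then telephone calls to non-responders. For some participants the visit may therefore have come before follow-up; the documents do not say for how many.

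The tailored text messages and the clinician insight are not rival causes. The Protocol's Design section makes them part of the refresh experience. They only prevent attribution to the app alone.

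The sentence covers the primary outcome. Read as written, it would let any significant change be reported as an effect of refresh.

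**Working it through.** **No figure to reproduce.** The documents state no alpha, power, target effect size, SD of change or number of completers. The reduction in sample size from 100 to 50 is given without a statistical derivation. The main check is therefore one of logic, with an illustration of scale.

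**What the test addresses.** Let D be a participant's day-30 score minus the baseline score. Then mean(D) = R + B, where R is the mean change caused by refresh and B is the mean change from everything else. The paired t-test has null hypothesis R + B = 0. A statement about R alone needs B to be known or estimated. The design supplies no estimate of B, so no value of the t statistic or of Cohen's d can isolate R.

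**Inputs to the illustration**
- n = 51 pairs: the number of participants in the Protocol's Methods, and so the most that can be analysed. Complete follow-up is an assumption.
- Two-sided alpha = 0.05: an assumption.
- R = 0: assumed, so that every significant result is due to background change.
- Shift δ = B / SD(D), from 0 to 0.4: an assumed range.

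**Formulas.** df = n − 1 = 50, and the critical value is t = 2.009. The noncentrality is λ = δ√n, with √51 = 7.141. The probability of significance is P(|T| > 2.009), where T is noncentral t with 50 df and noncentrality λ.

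| δ | λ = δ × 7.141 | Probability of p < 0.05 |
|---|---|---|
| 0 | 0 | 0.050 |
| 0.05 | 0.357 | 0.064 |
| 0.1 | 0.714 | 0.108 |
| 0.2 | 1.428 | 0.288 |
| 0.3 | 2.142 | 0.556 |
| 0.4 | 2.857 | 0.800 |

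A simulation of 200,000 runs for each non-zero shift gave 0.065, 0.107, 0.289, 0.558 and 0.799.

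**Smallest significant change.** 2.009 / √51 = 0.281. An observed mean change of about 0.28 SD of the change score or more is significant whatever caused it.

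**Fewer completers (assumed numbers).** For shifts of 0.2, 0.3 and 0.4 SD, the probabilities are 23.5%, 45.7% and 69.4% with 40 pairs, and 18.5%, 35.5% and 56.3% with 30 pairs.

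The first row shows that the test keeps its nominal 5% error rate for the hypothesis of no change. The other rows show that it offers no such protection for the hypothesis of no effect of refresh.

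**The case against.** The strongest reply is that this is one loose phrase among neutral text. The preceding sentence names the single-group design, the following one defines the outcome as change, and Cohen's d is tied to differences. The Protocol sets an acceptability and feasibility purpose for a Phase I pilot. There is no efficacy hypothesis, success threshold or go/no-go rule that depends on these p-values. The study appears complete, so only reporting language is at issue, and the correction changes no number. This is fair, and it limits the weight of the point. It does not make the sentence true: it says determine, it names refresh as the cause, it applies to the primary outcome, and no text elsewhere limits attribution.

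The illustration is also the generic power curve of a one-sample t-test at the largest possible n. That stands: the documents give no evidence that expectancies drift over 30 days, and the percentages fall with fewer completers. The logical point needs none of these figures.

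Finally, some rival causes are possible rather than shown. Eligibility sets no threshold on expectancies or confidence, so regression to the mean is not built in by selection. The clinic visit is partly intertwined with refresh, because the clinician insight is written to guide it. Both qualifications stand. They weaken individual explanations but provide no estimate of background change.

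**Conclusion.** The concern holds. The SAP attributes to its paired t-tests a conclusion that its own design cannot support, and the sentence should be corrected. Under the stated assumptions, background change alone would produce significance in about 6% of studies at a shift of 0.05 SD and about 80% at 0.4 SD, so small shifts matter little and larger ones a great deal. Which applies here is unknown.

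The conclusion is limited. It does not say that the t-test is invalid for mean change, that refresh had no effect, or that this pilot needed a control group. It says that the design does not support attributing the change to refresh, whatever the size of the background shift.

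**What to change.** Replace the SAP sentence with wording such as:

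> Paired t-tests estimate and test the within-participant change from baseline to 30-day follow-up. With no control group, this change cannot be attributed to refresh, and Cohen's d describes the pre-post change.

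Add a statement that no efficacy claim will be made from these p-values, and carry the same language into the study report. This brings the SAP into line with the Protocol's own description of the tests.

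The cost is confined to wording in the SAP and report, and the stated conclusion becomes less favourable. No new data, tests or estimates are needed.

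### Does the SAP need a multiplicity rule because it applies paired t-tests to an open list of secondary outcomes?

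*SAP*

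**What the plan says.** The SAP's only analysis section treats both tiers of outcome in one sentence: "Paired t-tests were used to determine the effect of the *refresh* intervention on the primary and secondary outcomes". It then fixes a single primary outcome: "The primary outcome was change, from pretest (baseline) to posttest (30 day follow-up), in psychosocial expectancies for smoking". The secondary tier is introduced without being closed: "Secondary outcome measures include change in confidence to quit smoking between pretest (baseline) and posttest (30 day follow-up) assessments". Beyond the test, the SAP adds only an effect size: "Cohen's d was used to assess the magnitude of the differences".

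The closing analysis paragraph of the protocol is consistent with this and equally open about the number of tests: "Paired t-tests of pre-post differences on several key outcomes, including the primary outcome (psychosocial expectancies) were conducted". Under Methods, the protocol lists what was measured at baseline, including "current rate of tobacco use, psychosocial expectancies, self-efficacy, and readiness to quit smoking, tobacco products, and e-cigarettes", but does not say which of these were repeated at 30 days. On size it reports: "Fifty-one individuals participated in the pilot test". Under Objective and Design it describes a 30-day, single-group pre-post pilot, labelled Phase I, that is meant to assess acceptability and feasibility.

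Neither document states a significance level, sidedness, number of tests, testing order, adjustment, or whether secondary results are exploratory.

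**The concern.** Using a test to determine an effect is confirmatory language, and the SAP extends it to secondary outcomes on the same terms as the primary. The protocol's reference to several outcomes suggests more tests than the two that are named. Read literally, a small p-value on any of them might be reported as an effect of the app, and a reader could not tell one significant result among two from one among six.

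Two things would be at stake. The first is a raised chance of at least one false positive across the set. The second is selection: if the best-looking secondary result were singled out, its Cohen's d would be too large on average, and anyone planning later work from it would be misled.

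**Working it through.** **Inputs.** From the documents: one primary outcome, at least one secondary outcome, and 51 participants. The number with paired follow-up data is not given. Assumed, because neither document states it: a two-sided 5% level per test. The documents offer no error rate to reproduce.

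**Primary outcome.** There is one test, so the false-positive chance is the level of that test (5% under the assumption), however many secondary tests are run.

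**Secondary outcomes.** For *k* independent tests at level α with no true change, the chance of at least one significant result is 1 − (1 − α)^k.

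| Secondary tests | Independent | Correlation 0.5 | Correlation 0.8 |
|---|---|---|---|
| 1 (the one named) | 1 − 0.95 = 5.0% | 5.0% | 5.0% |
| 2 | 1 − 0.95² = 9.8% | 9.0% | 7.8% |
| 5 | 1 − 0.95⁵ = 22.6% | 18.4% | 12.8% |

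The correlated values for two and five tests come from simulated paired t-tests with 51 pairs (100,000 replicates). With 30 pairs they barely move: 9.0% and 7.9% for two tests, 18.6% and 13.0% for five.

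The row for two follows from reading *several* as three outcomes including the primary. The row for five treats every repeatable baseline measure as a tested outcome and counts readiness as three separate targets. The documents support neither step, so that row is an illustration only.

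**Primary and secondary pooled.** Counting the two named outcomes together gives 1 − 0.95² = 9.8% if independent. This describes the event that either one is significant. The SAP sets no success criterion of that kind.

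**Sensitivity to the assumed level.** For two tests at 0.025, 1 − 0.975² = 4.9%. For five tests at 0.01, 1 − 0.99⁵ = 4.9%. So whether the pooled chance exceeds 5% depends on a level the documents do not state.

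**Direction.** If only favourable results count as claims of benefit, each two-sided 5% test contributes 2.5%. Two independent tests then give 1 − 0.975² = 4.9% and three give 1 − 0.975³ = 7.3%.

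**Selection effect on Cohen's d.** Under no change and independence, with 51 pairs, the mean of the largest favourable secondary d is 0.00 for one outcome, 0.08 for two and 0.17 for five. At correlation 0.5 these become 0.00, 0.06 and 0.12. For scale, the smallest |d| reaching p < 0.05 with 51 pairs is 0.28. For the named secondary outcome alone there is no selection and no bias from it.

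**The case for a change.** The best argument for a change is that the pilot label does not reach the analysis text. The SAP names an efficacy-type primary outcome, uses tests to establish an effect, and nowhere says that secondary results carry less weight. One sentence would settle the matter at almost no cost, and without a count of tests no reader can judge an isolated significant result.

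Part of this stands. The list is open, no status is assigned to the secondary results, and a complete list of pre-post comparisons would make the report easier to read. But the rule that any small p-value counts as an effect is inferred: the SAP gives no threshold and no any-outcome criterion, and it does not provide for highlighting the best result. The larger inflation figures need five secondary tests, a number assembled from the baseline list and not stated anywhere, and independence between measures taken on the same people, which is the extreme case.

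The possible remedies do not amount to correcting an error either. An exploratory label writes down the ordinary reading of secondary outcomes in a small uncontrolled pilot. A Holm adjustment is a matter on which competent statisticians would differ here, since it gives up power in a study not meant to confirm anything. Because the data are already collected, neither could be presented as pre-specified.

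**Conclusion.** No change to the plan is called for. The observation about the text is accurate: the secondary list is open, and no level, count or status is stated. The consequence is small. The primary test and the one named secondary test each keep their own level. With two secondary outcomes, the chance of a false-positive secondary result is at most about 10%, and lower if they are correlated. This rests on an assumed two-sided 5% per test and an assumed count; the documents give neither.

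This is a gap that analysts fill sensibly when they report: show every pre-post outcome tested with its mean change, 95% confidence interval and the planned Cohen's d, treat the secondary ones as exploratory, and say that this labelling came after data collection. Whether to adjust formally for multiplicity in a pilot of this kind is a fair trade-off, and leaving the secondary tests unadjusted is a defensible choice.

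### Does the SAP need changing because it pairs t-tests with Cohen's d but mentions no confidence interval and does not name the SD behind d?

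*SAP*

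**What the plan says.** The SAP is one paragraph under the heading Statistical Analysis Plan. It describes the design, "This study involved a single-group, pre-post design", and names one primary outcome: "The primary outcome was change, from pretest (baseline) to posttest (30 day follow-up), in psychosocial expectancies for smoking". Change in confidence to quit is secondary. The analysis is by paired t-test, and the last sentence reads "Cohen's d was used to assess the magnitude of the differences".

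The closing analysis paragraph of the Protocol agrees: "Paired t-tests of pre-post differences on several key outcomes, including the primary outcome (psychosocial expectancies) were conducted". It adds descriptive statistics for the sample, app use and acceptability, and qualitative coding of open-ended answers. The Protocol's Methods record an approved "reduction in sample size from 100 to 50 participants" and state that "Fifty-one individuals participated in the pilot test".

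Neither document mentions a confidence interval, the SD that standardises d, the pre-post correlation, a significance level, a power or precision target, or the number of complete pairs. The Protocol's Objective gives the purpose as acceptability and feasibility.

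**The concern.** Cohen's d has no single definition in a paired design. It may be the mean change divided by the SD of change (d_z below), by the baseline SD, or by an average of the two raw SDs (d_raw). The first follows directly from the t statistic, so it is an easy default. When pre and post scores are strongly correlated it is larger than the raw-SD versions. A reader who set it against the usual small, medium and large benchmarks, or carried it into planning a two-group trial, would then think the change bigger than it is.

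The second worry is precision. A pilot's useful quantitative product is an estimate with its uncertainty. A point value of d from about 50 people hides how loosely it is pinned down, and a non-significant test could be read as showing no change. Halving the sample makes both worse, and the Protocol says that several outcomes are tested.

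**Working it through.** **Inputs.** From the documents: planned size 100, revised to 50; 51 participants; paired t-test; Cohen's d with no stated SD. Assumed, because the documents are silent: two-sided 5% level and 95% intervals; pre-post correlation r from 0.3 to 0.9; equal pre and post SDs; 30 to 51 complete pairs.

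**Plan's own figure.** Neither 100 nor 50 can be reproduced, since no effect size, SD or power is given. Only the halving can be checked: 50/100 = 0.5.

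**Scale of d.** With equal SDs, SD of change = SD × √(2(1 − r)), so d_z / d_raw = 1/√(2(1 − r)).

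| r | d_z / d_raw |
|---|---|
| 0.3 | 0.85 |
| 0.5 | 1.00 |
| 0.6 | 1.12 |
| 0.7 | 1.29 |
| 0.8 | 1.58 |
| 0.9 | 2.24 |

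An inflation of 1.3 to 1.6 fold requires r between 1 − 1/(2 × 1.3²) = 0.70 and 1 − 1/(2 × 1.6²) = 0.80, and also requires that d uses the SD of change. At r = 0.5 the two agree. Below that, d_z is the smaller.

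**Precision.** 95% intervals for d_z, by inverting the noncentral t distribution:

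| Pairs | d_z = 0.40 | d_z = 0.50 |
|---|---|---|
| 100 | 0.20 to 0.60 | 0.29 to 0.71 |
| 51 | 0.11 to 0.68 | 0.21 to 0.79 |
| 40 | 0.08 to 0.72 | 0.17 to 0.83 |
| 30 | 0.03 to 0.77 | 0.12 to 0.88 |

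For values of 0.2 to 0.5 the half-width is about 0.28 to 0.29 with 50 pairs and 0.20 to 0.21 with 100. That is close to the factor √(100/50) = 1.41 expected from halving. The d_z detectable with 80% power moves from 0.28 to 0.40.

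These widths apply to d_z only. In simulation with a true d of 0.3 and 50 pairs, the half-width for d on the averaged raw SD is 0.33 at r = 0.3, 0.29 at 0.5, 0.22 at 0.7 and 0.19 at 0.8. At the correlations that produce the 1.3 to 1.6 fold ratio, the raw-SD d is therefore better determined than the d_z intervals suggest.

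**What the t-test already carries.** The statistic is t = mean change / (SD of change/√n), and the 95% interval is mean change ± t_crit × SD of change/√n. The quantities are the same. Take d_z = 0.40 with 51 pairs:

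- t = 0.40 × √51 = 2.86.
- t_crit/√51 = 0.281.
- In units of the SD of change, the interval for mean change is 0.40 ± 0.281, or 0.12 to 0.68. The noncentral-t interval for d_z is 0.11 to 0.68.

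A results table with pre and post means and SDs, t and n gives the rest. SD of change = mean change × √n / t, and r = (SD_pre² + SD_post² − SD_change²)/(2 × SD_pre × SD_post). Any version of d can then be computed.

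**The case for a change.** The best case for a change is that it costs almost nothing. A few words would name the SD behind d and promise intervals. Without them, a reader given d alone cannot tell which of several numbers it is, and at this sample size the point value is weak evidence. An acceptability and feasibility pilot has all the more reason to estimate and not to test, yet the SAP uses t-tests to judge the effect.

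Part of this stands. No interval is mentioned, the standardiser is undefined, and precision with 51 pairs or fewer is limited. A good report would give the mean change with its 95% interval, say which SD was used, and state the number of pairs.

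The rest does not reach the plan. Inflation is a possibility that depends on two unstated facts, and it reverses when r is below 0.5. d_z is a recognised measure; it misleads only when read on the wrong scale, and neither document sets d against benchmarks or uses it to size a later trial. The shift in detectable effect from 0.28 to 0.40 misses no target, because none is stated. No previous analysis text is shown that the smaller sample should have altered. One primary outcome is named, so the mention of several outcomes does not leave the main comparison open. Choosing the baseline SD, or dropping tests on secondary outcomes, is a preference on which experienced statisticians differ.

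**Conclusion.** No change to the plan is called for. Followed as written, it yields a valid paired test of the primary outcome and an accepted effect size. The interval for mean change follows from the same output, and whichever SD is chosen for d leaves the test result unaltered.

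The silence on the standardiser matters only for interpreting d. If d uses the SD of change, it is 0.85 to 2.24 times the raw-SD d for r from 0.3 to 0.9, assuming equal SDs. The imprecision (half-width about 0.28 to 0.29 for d_z with 50 pairs) comes from the sample size, and no wording in the SAP would reduce it. Both documents are written in the past tense about completed work, so what remains open is how the results are presented, and there the missing details are routine.

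These figures rest on the assumed 5% two-sided level and on 50 or 51 complete pairs as the best case. The view would change if a report set a change-score d against raw-score benchmarks, or sized a two-group trial from it, without giving the correlation. Nothing in the documents does so.
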